13.4.5. Descriptive Analyses

Descriptive statistics will be provided for participant disposition, baseline and demographic characteristics, study drug compliance, and use of concomitant medications. Continuous measures will be summarized using n, mean, standard deviation (SD), median, minimum, and maximum. Categorical variables will be summarized using counts and percentages.

13.5. Interim Analyses

Other than interim looks by the DSMB to review data on safety and study conduct, no interim analyses are planned for either efficacy or futility.

13.6. Statistical Hypothesis

See Section 13.4.2, *Primary Analysis of Primary Endpoint*.

13.7. Sample Size Considerations

Preliminary data for the sample size computations are derived from a study that examined UVB-induced apoptosis of keratinocytes derived from individuals with cutaneous lupus before and after exposure to baricitinib, a Jak inhibitor like tofacitinib[6]. Although this study examined in vitro exposure of cultured keratinocytes, apoptotic percentages are expected to be similar to skin since UVB is penetrant to the basal keratinocyte layer in vivo. Estimates for means and SDs are presented in Table 13.1.

Table 13.1: Estimates for mean (SD) for Percentage of apoptotic keratinocytes that were unexposed, UVB-exposed with no drug, and UVB-exposed with baricitinib

	Percentage of apoptotic keratinocytes			
	unexposed [1]	UVB only [2]*	UVB + drug [3]*	[3]*
	$A_{\text{unexposed}}$	A_{pre}	A_{post}	$A_{\text{post}} - A_{\text{pre}}$
n	6	11	5	5
Mean	6%	50%	16%	-37%
SD	6%	14%	9%	15%
80% CI for SD	(4.4%, 11%)	(11%, 20%)	(6.5%, 17%)	(11%, 30%)

[1] Data points derived from Fig 6B of Sarkar et al (2018) [6].

[2] Data points derived from Fig 6B and Fig 6E of Sarkar et al (2018) [6].

[3] Data points derived from Fig 6E of Sarkar et al (2018) [6].

*5 of these samples were paired.

Since $A_{\text{unexposed}}$ is expected to be similar at pre and post-treatment time points, the change in $A^{\text{UVB}} = A_{\text{post}} - A_{\text{pre}}$ is approximately equal to $A_{\text{post}} - A_{\text{pre}}$. As such, the SD for $A_{\text{post}} - A_{\text{pre}}$ for the preliminary data, 15% (Table 13.1), is used as starting point for power calculations. Power estimates for a design with 10 participants were computed over a range of possible means for change in A^{UVB} , and for different distribution assumptions (normal, logistic, double exponential and uniform; Figure 2). For this study, an improvement (decrease) from pre- to post-treatment of at least 20 percentage points is considered relevant for demonstrating proof-of-concept. For the best estimate of SD, 15%,

power is $\geq 93\%$ for a mean change in A^{UVB} of at least 20 percentage points under all four distributions ($\alpha=0.05$, two-sided, Wilcoxon signed-rank test). Power is $\geq 80\%$ under all 4 distributions for a mean change in A^{UVB} of at least 21.4 percentage points as long as the $SD \leq 20\%$. If the underlying SD is 30%, the upper 80% confidence limit from Table 13.1, the design has at least 80% power to detect a change of at least 30 percentage points under the uniform, logistic, and double exponential distributions, and 32.1 percentage points under the normal distribution. Power was computed using PASS version 15.

[figure not shown]

Figure 2. Power for 10 paired samples (pre and post treatment) under different distribution assumptions

All participants completing Visit 5 (Day 26) skin biopsy will be included in the primary analysis of the primary endpoint. For the primary analysis, there will be no missing data; participants who cannot complete the second biopsy will be replaced. As such, missing data does not impact the power/sample size considerations, but attrition will be considered when evaluating generalizability of the results.

14. Identification and Access to Source Data

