13.4.2. Primary Analysis of Primary Endpoint

The primary endpoint is change in percentage of UVB-induced apoptotic epidermal cells from Visit 2 (Day 1) (pre-treatment) to Visit 5 (Day 26) (post-treatment). Percentage of UVB-induced apoptotic cells (A^{UVB}) is defined as the number of TUNEL positive cells in the epidermis divided by the number of nuclei in that high powered field. The percentage of UVB-induced apoptotic cells at a visit is defined as the difference between the percentage of apoptotic epidermal cells in the biopsy exposed at the MED ($A^{Day1MED}$) and percentage of apoptotic epidermal cells in the unexposed biopsy ($A^{unexposed}$), for both biopsies taken at the same visit. The change in percentage of UVB-induced apoptotic epidermal cells will be computed as follows for each individual in the study:

$$A_{Day\ 1}^{UVB} = A_{Day\ 1}^{Day1MED} - A_{Day\ 1}^{Day\ 1\ unexposed}$$

$$A_{Day\ 26}^{UVB} = A_{Day\ 26}^{Day1MED} - A_{Day\ 26}^{Day\ 26\ unexposed}$$

$$\text{change in } A^{UVB} = A_{Day\ 26}^{UVB} - A_{Day\ 1}^{UVB}$$

The null and alternative hypotheses for the primary analysis of the primary endpoint are:

H_0 : Mean change in $A^{UVB} = 0$

H_A : Mean change in $A^{UVB} \neq 0$

The statistical hypotheses outlined above for the mean change in A^{UVB} will be evaluated in the PP1 population using a two-sided Wilcoxon signed-rank test at a Type 1 error rate of 0.05.

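### The 15% SD behind the stated power of at least 93% omits the two unexposed biopsies in the primary endpoint, so that power figure is unsupported and may be overstated

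*Combined protocol and SAP*

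**What the plan says.** Section 13.4.2 builds the primary endpoint from four biopsies. At each visit the unexposed percentage is subtracted from the percentage at the Day 1 MED dose, "for both biopsies taken at the same visit", and the Day 1 difference is then subtracted from the Day 26 difference. The mean change "will be evaluated in the PP1 population using a two-sided Wilcoxon signed-rank test at a Type 1 error rate of 0.05".

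Section 13.7 takes its inputs from an in vitro study of cultured keratinocytes (Table 13.1). It reasons that the unexposed percentage "is expected to be similar at pre and post-treatment time points", treats the endpoint as approximately A_post - A_pre, and says that the SD of that two-sample change "for the preliminary data, 15% (Table 13.1), is used as starting point for power calculations". The same section later calls 15% the best estimate of the SD. A fall "of at least 20 percentage points is considered relevant for demonstrating proof-of-concept". With 10 participants and an SD of 15%, power is given as at least 93% for a mean change "of at least 20 percentage points under all four distributions". The text also reports SDs of 20% and 30%, but at larger effects: 21.4 points, and 30 to 32.1 points.

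**The concern.** The 15% is the SD of a change between two exposed samples. The endpoint adds two unexposed biopsies, each with its own measurement error. Expecting the unexposed values to be alike on average means that they cancel from the mean change. It says nothing about their spread, and Table 13.1 shows that the spread is not zero.

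A stable personal background level already cancels in A_post - A_pre. Subtracting two further biopsies can therefore add visit-to-visit noise, unless exposed and unexposed biopsies from one visit share some error that the subtraction removes. The plan makes no such argument.

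The figure at stake is the study's headline power at its own proof-of-concept threshold. It has almost no margin: by the method that reproduces the plan's figures, 93% under all four distributions holds only up to an SD of about 15.2%.

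**Working it through.** **Inputs.** From 13.7: n = 10, two-sided alpha 0.05, Wilcoxon signed-rank test, target 20 points, four distributions (normal, logistic, double exponential, uniform). From Table 13.1: SD of A_post - A_pre 15% (5 pairs, 80% CI 11% to 30%); unexposed SD s_u = 6% (n = 6, 80% CI 4.4% to 11%). The documents give no correlations, so these are assumptions below.

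**Reproducing the plan.** Noncentral-t power for a one-sample test, with n divided by the usual Wilcoxon factor and rounded down (1 uniform, 2/3 double exponential, 9/pi^2 logistic, pi/3 normal), gives effective n of 10, 15, 10 and 9. At 20 points and SD 15%, power is 96.2%, 99.8%, 96.2% and 93.7%. The minimum agrees with the stated 93%. The same method gives 80.2% under normal at 21.4 points with SD 20% and at 32.1 points with SD 30%, and 80.3% under uniform and logistic at 30 points with SD 30%. These match the plan's other figures.

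As a cross-check I simulated the exact test (reject if the smaller rank sum is at most 8, true alpha 0.0488). At 20 points and SD 15% it gives 92.4% to 95.8%.

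**SD of the endpoint as defined.**

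SD = sqrt(15^2 + 2 x s_u^2 x (1 - rho) - 2 x Cov)

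Here rho is the correlation of a person's two unexposed values, and Cov is the covariance of the exposed change with the unexposed change.

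**With Cov = 0, at 20 points:**

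| s_u | rho | SD | Lowest of four distributions, noncentral t | Exact test, range over four |
|---|---|---|---|---|
| 6% | 1 | 15.0% | 93.7% | 92-96% |
| 6% | 0.5 | sqrt(225 + 36) = 16.2% | 90.0% | 90-92% |
| 6% | 0 | sqrt(225 + 72) = 17.2% | 86.1% | 87-89% |
| 11% | 0 | sqrt(225 + 242) = 21.6% | 68.3% | 66-75% |

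At SD 17.2% the noncentral-t figures are 86.1% normal, 90.3% uniform and logistic, and 98.6% double exponential.

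**With Cov above 0.** The SD returns to 15% when Cov = s_u^2 x (1 - rho).
- s_u = 6%, rho = 0: Cov = 36, and the SD of the unexposed change is sqrt(72) = 8.49, so the break-even correlation is 36 / (15 x 8.49) = 0.28.
- s_u = 6%, rho = 0.5: Cov = 18, and the SD of the unexposed change is 6, so it is 18 / (15 x 6) = 0.20.
- s_u = 6%, rho = 0, correlation 0.5: SD 13.0%.
- Background fully shared and additive (Cov = 72): SD = sqrt(225 - 72) = 12.4%, lowest power 98.8%.

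**With Cov below 0.** At s_u = 6%, rho = 0 and correlation -0.3, the SD is 19.3% and the lowest power is 77.6%.

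**The plan's larger SDs.** At SD 20%, power at the 20-point target is 74.8% under normal (noncentral t) and 73-80% by the exact test. The text of 13.7 does not report it.

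**The case against.** The strongest reply is that the direction of the error is unknown. Each exposed biopsy is paired with an unexposed one from the same visit and the same side of the body (8.5.5), so a shared visit effect is plausible. A moderate one would cancel the added variance or more. This stands. A reader might infer that power is definitely overstated, or that 15% is the best case. The documents support neither, because a positive covariance takes the SD below 15%.

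A reader might also want to put 17% in place of 15%. That goes too far as well. It needs rho = 0 and Cov = 0, and it treats the whole spread of six in vitro values as visit-to-visit noise within a person.

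The plan does hedge. It calls the equality approximate and the SD a starting point, and its 20% and 30% scenarios bracket both 17.2% and 21.6%. Figure 2 is not visible here and may show more. But in the text those scenarios are tied to effects above 20 points, so they do not give the power at the stated threshold.

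Finally, the plan discloses a larger uncertainty. The 15% rests on five pairs with an 80% interval of 11% to 30%, and against that 15% versus 17.2% is small. That bears on materiality, but it does not make similar means a reason to drop a variance.

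**Conclusion.** The point holds in conditional form. The plan's power arithmetic reproduces, but it is applied to the SD of a different quantity from the primary endpoint, and the reason given covers only the mean. The statement of at least 93% power at 20 points is therefore unsupported and may be too high.

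At the table's 6% and with zero covariance, the loss runs from nothing to about 8 percentage points on the plan's own basis (lowest power 93.7% down to 86.1%). Power stays above 80% throughout that range. It falls below 80% with independent unexposed biopsies at the 11% limit, or with a negative covariance such as the one shown above. With enough positive covariance there is no overstatement. The documents give neither correlation, so no single replacement SD can be derived from them. Nothing here shows that 10 participants are too few.

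**What to change.** In 13.7:
- Say that 15% is the SD of the exposed change only, and that power of at least 93% holds only if the unexposed terms add no net variance.
- State the assumed correlation between a person's two unexposed values, and between the exposed and unexposed changes.
- Report power at the 20-point target for SDs of about 15% to 22%, all by one method. By the approximation that matches the plan's figures, the entry at 17.2% (independent unexposed biopsies, zero covariance) would be about 86% under normal and 90% under uniform and logistic, with double exponential higher. By the exact test it would be 87-89%. The two sets should not be mixed in one table.
- Redraw Figure 2 to match if it does not already show these SDs at 20 points.

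Keep n = 10. The cost is wording and possibly one figure, with a slightly less favourable stated power. No participants, visits or biopsies are added.

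### Section 13.7 claims at least 80% power for a 30-point change at SD 30% under the uniform distribution; the planned signed-rank test with 10 participants has about 73%

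*Combined protocol and SAP*

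**What the plan says.** Section 13.4.2 tests the primary endpoint, the change in the percentage of UVB-induced apoptotic epidermal cells, "using a two-sided Wilcoxon signed-rank test at a Type 1 error rate of 0.05". Section 13.7 gives power for 10 participants under normal, logistic, double exponential and uniform distributions, and names the same test there ("two-sided, Wilcoxon signed-rank test").

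It makes three power statements:

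- SD 15%: at least 93% for 20 points under all four distributions.
- SD up to 20%: at least 80% for 21.4 points under all four.
- SD 30%, introduced by "If the underlying SD is 30%, the upper 80% confidence limit from Table 13.1". For three of the four shapes the claim is "at least 80% power to detect a change of at least 30 percentage points under the uniform, logistic, and double exponential distributions". The fourth shape is given a higher threshold for the same power: "and 32.1 percentage points under the normal distribution".

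On method it says only "Power was computed using PASS version 15". It gives no formula, option or approximation.

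**The concern.** For a fixed distribution shape and sample size, signed-rank power depends only on the ratio of the mean change to the SD. The SD 30% sentence therefore fixes a ratio of 30/30 = 1.00 for three distributions and 32.1/30 = 1.07 for the normal, and every input needed to check it is in the document.

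Two things look wrong. The 80% attached to the uniform at ratio 1.00 equals ordinary paired-t power at that ratio. And the uniform is placed among the distributions that need a smaller change than the normal, which need not be so for a rank test on 10 differences.

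This sentence tells the reader how the design holds up if the SD is much larger than planned. If the uniform figure is wrong, it credits the planned test with power it does not have and lists the least favourable shape among the favourable ones.

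**Working it through.** **Inputs.** Two-sided signed-rank test at 0.05 (Sections 13.4.2 and 13.7); n = 10 paired differences; SD 30 points; change 30 points, or 32.1 for the normal; no allowance for dropout, because participants without a second biopsy are replaced (all Section 13.7).

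**Step 1: reproduce the plan's figures.** All of them can be recovered from a large-sample approximation: two-sided t-test power with n replaced by n′ = floor(10/W). W is the efficiency factor of the signed-rank test against the t-test: uniform 1, normal π/3, logistic 9/π², double exponential 2/3. This gives n′ = 10, 9, 10 and 15. Power is P(|T| > t₀.₉₇₅,n′₋₁), where T is noncentral t with n′ − 1 degrees of freedom and noncentrality (change/SD)·√n′.

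| Statement | Approximation gives | Plan states |
|---|---|---|
| Uniform and logistic, 30/30, n′ = 10 | 80.3% | ≥80% |
| Double exponential, 30/30, n′ = 15 | 94.9% | ≥80% |
| Normal, 32.1/30, n′ = 9 | 80.2% | ≥80% |
| Normal, 21.4/20, n′ = 9 | 80.2% | ≥80% |
| Normal, 20/15, n′ = 9 | 93.7% | ≥93% |

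For the uniform, W = 1, so the approximation is simply paired-t power at n = 10. That the software worked this way is inferred from the match; the document does not say so.

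**Step 2: rejection rule of the planned test.** Over the 2¹⁰ = 1024 sign patterns, the smaller rank sum is at most 8 in 50 patterns (50/1024 = 0.0488) and at most 9 in 66 (66/1024 = 0.0645). At a two-sided 0.05 level the rule is therefore to reject when the smaller rank sum is 8 or less.

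**Step 3: power of that test.** Simulation with each distribution scaled to the stated SD. The 20/15 and 30/30 columns, and the normal at 1.07, use 2,000,000 trials per case (error at most 0.03 points); the other 1.07 entries use 1,000,000.

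| Distribution | 20/15 = 1.333 | 21.4/20 = 32.1/30 = 1.07 | 30/30 = 1.00 |
|---|---|---|---|
| Uniform | 95.8% | 79.6% | **73.1%** |
| Normal | 95.4% | 83.6% | 78.5% |
| Logistic | 94.2% | 83.9% | 79.5% |
| Double exponential | 92.4% | 83.3% | 79.7% |

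A separate simulation of 1,000,000 trials gave 73.2% for the uniform at 1.00.

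**Step 4: could another version of the test give 80%?** For the uniform at ratio 1.00:

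- normal approximation without continuity correction: 73.2%
- normal approximation with continuity correction: 68.6%
- cut-off of 9: 78.2%, but with size 0.0645
- one-sided 0.05: 83.1%
- paired t-test: 80.3%

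No signed-rank version tried with two-sided size at or below 0.05 reaches 80%.

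**Step 5: change needed for 80% at SD 30%.** Ratios found by bisection, times 30:

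| Distribution | Ratio × 30 | Points needed | Plan states |
|---|---|---|---|
| Uniform | 1.0747 × 30 | 32.2 | 30 |
| Normal | 1.0194 × 30 | 30.6 | 32.1 |
| Logistic | 1.0063 × 30 | 30.2 | 30 |
| Double exponential | 1.0058 × 30 | 30.2 | 30 |

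Rounded up, 32.3 points cover all four. Equivalently, under the uniform a 30-point change has 80% power only if the SD is at most 30/1.0747 = 27.9%.

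**The case against.** The strongest reply is that nobody made a slip. One standard approximation reproduces every figure in the section, including the placing of the normal behind the uniform, so the numbers are consistent with each other and were probably software output. That stands as an explanation. It does not rescue the statement: Section 13.7 presents the figures as signed-rank power without mentioning an approximation, and an efficiency ratio derived for large samples is inaccurate with 10 differences and an effect of one SD.

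The second reply is that the affected case is remote. A uniform with SD 30 has half-width √3 × 30 = 52 points, so a mean change of −30 implies changes spread evenly from about −82 to +22. Table 13.1 puts UVB-induced apoptosis before treatment near 50 − 6 = 44 points, yet (82 − 50)/104, about 31%, of that uniform lies below −50. This is a fair point about plausibility and it limits the importance of the error. But the plan itself chose to report this combination.

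The third reply is that nothing else moves: the SD 20% statement holds to within half a point (79.6% to 83.9%), and conduct, analysis and sample size are unaffected. That is correct.

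**Conclusion.** The concern holds, as a minor error. At SD 30% and a 30-point change, the planned test with 10 participants has about 73% power under the uniform distribution, not at least 80%. At this SD the uniform needs a larger change than the normal, not a smaller one. The logistic and double exponential figures are within about half a point of 80%, and the normal statement is true but conservative (83.6% at 32.1 points).

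The result assumes the two-sided signed-rank test at 0.05, 10 untied differences, and each distribution scaled to the stated SD; all of these except the absence of ties are stated in the plan. No cause is asserted, since the document names only the software. The headline case stands at 92.4% to 95.8%, where the uniform is the most favourable of the four, and the sample size of 10 is not called into question.

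**What to change.** Replace the SD 30% sentence in Section 13.7 with exact or simulated signed-rank power for n = 10, for example: *At SD 30% and a 30-point change, power is about 73% (uniform), 78% (normal) and just under 80% (logistic, double exponential); 80% under all four distributions needs about 32.3 points.* Check the uniform curve in Figure 2, which is not in the text available here, by the same computation.

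So that the section does not mix two methods, it would be sensible to give the other two statements on the same basis: 92.4% to 95.8% for 20 points at SD 15%, where the double exponential falls just short of the stated 93%, and 79.6% to 83.9% for 21.4 points at SD 20%.

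The cost is text only. The uniform figure becomes less favourable, the normal one slightly more so, and the sample size does not change.

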14.1. Source Data

Source documents and source data are considered to be the original documentation where participant information, visits consultations, examinations and other information are recorded. Documentation of source data is necessary for the reconstruction, evaluation, and validation of clinical findings, observations, and other activities during a clinical trial.

14.2. Access to Source Data

The site investigators and site staff will make all source data available to the DAIT/NIAID, NIAID representatives, agents, employees, contractors, and other persons assisting in conducting, monitoring, or analyzing the study, as well as to relevant health authorities. Authorized representatives as noted above are bound to maintain the strict confidentiality of medical and research information that may be linked to identified individuals.

15. Quality Assurance and Quality Control

The principal investigator is required to keep accurate records to ensure that the conduct of the study is fully documented. The principal investigator is required to ensure that all eCRFs are completed for every participant entered in the trial. The period of record retention should be consistent with the record retention policies of the sponsoring agency or applicable regulatory agencies. However, in certain instances, documents should be retained for a longer period if required by the applicable regulatory agency or by the National Institutes of Health.

Data will be obtained from a variety of sources including, but not limited to laboratory notebooks, automated instrument output files, and clinical participant charts. Data from these source materials will be transmitted to the DAIT data center via one of two mechanisms. Data collected electronically at central laboratories will be transferred electronically directly from the laboratory to the DAIT data center using standard secure data transfer procedures. Data collected at the clinical site will be transmitted to the DAIT data center using an internet-based remote data entry system. Clinical site personnel use an internet browser to key data into eCRFs; each CRF page is submitted to the clinical database electronically as the page is completed. Univariate data validation tests are performed as the data are keyed. The clinical database is backed up nightly; backup tapes are saved in a secure, off-site location. At any time, authorized site personnel may log in to the remote data entry system, review and correct previously entered data, or key additional data. The data will be further validated per the study data validation plan via a series of computerized and manual edit checks, and all relevant data queries will be raised and resolved on an ongoing basis. Complete, clean data will be frozen to prevent further inadvertent modifications. All discrepancies will be reviewed, and any resulting queries will be resolved with the investigators and amended in the database. All elements of data entry (i.e., time, date, verbatim text, and the person performing the data entry) will be recorded in an electronic audit trail to allow all data changes in the database to be monitored and maintained in accordance with federal regulations.

Monitors are responsible for regular inspection of the conduct of the trial, for verifying adherence to the protocol, and for confirming the completeness, consistency, and accuracy of all documented data.

Monitors will periodically visit the participating clinical site and audit the source documents in order to validate the data in the central database. Data will be provided using the participant's screening or enrollment number, the DAIT data center will not collect personally identifying information such as the participant's name or social security number. Participants will provide demographic information such as race, ethnicity, and birth date.

Data collected by the DAIT data center will be held in the strictest confidence and are protected from access that could reveal personally identifying information about any participant in the trial.

16. Protocol Deviations

